### *2.5. Blood Collection and Pretreatments*

Fasted blood samples were collected at months 0, 3, and 6. The blood samples (80 mL) from subjects who fasted for 12 h were used to determine biomarkers for bone metabolism. Whole blood samples were collected in serum tubes (BD Vacutainer,

Mississauga ON, Canada), centrifuged at  $3500\times g$  for 15 min at 4 °C, divided into aliquots, and stored at -80°C until analyzed.

#### *2.6. Measurements of Serum Biomarkers of Bone Metabolism*

Changes in the amino-terminal propeptide of type 1 procollagen (P1NP), bone-specific alkaline phosphatase (BALP), osteocalcin (OC), carboxy-terminal crosslinked telopeptide of type 1 collagen (CTX1), and sclerostin at baseline, 3 months, and 6 months were measured in serum using commercially available ELISA kits.

### **3. Statistical Analysis**

Data are reported as mean  $\pm$  standard deviation (SD) unless specified otherwise. Differences with two-sided  $p < 0.05$  were considered significant. Data were analyzed using analysis of variance methods with PROC MIXED in SAS (Version 9.4, SAS Institute, Cary, NC, USA) to determine the main and interaction effects of the two factors, treatment (0, 392, or 784 mg/day blackcurrants), and time (baseline, 3 months, and 6 months). The significance of differences in baseline characteristics was tested by ANOVA or Chi-square/Fisher's Exact test. The significance of changes in all outcome variables was tested by repeated-measures ANOVA with treatment as levels of between-subjects factors and time as levels of within-subjects factors. Percent changes in BMD and bone biomarkers between control and low BC groups and between control and high BC groups were evaluated using *t*-tests.

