### **2.2. Study Design**

Upon signing the consent form, an initial physical examination (body weight, height, waist circumference, and blood pressure) was conducted. The participants were also interviewed about their medical history and dietary behaviors by study personnel. Participants had a urine pregnancy test to confirm that they were not pregnant and thus eligible for the bone density measurement using dual-energy X-ray absorptiometry (DXA). All eligible participants completed an additional consent form for the DXA

assessment and scheduled their bone mass measures on or within  $\pm$  3 days of study visit 1 (month 0) and 3 (months 6) at the University of Connecticut Korey Stringer Institute Human Performance Laboratory. Participants were asked to refrain from taking the provided calcium supplements the day before the exam (24 h) to limit potential interference with the DXA measurements.

The participants were taught how to complete 3-day food records (FR) and physical activity records and asked to complete them one week prior to each study visit at months 0, 3, and 6. Subjects who were taking any dietary supplements that are known to affect bone metabolism were asked to stop taking them. After the initial screening visit, subjects underwent a 2-week equilibration period, followed by a 6-month clinical trial period. To avoid potential bone deterioration related to calcium and vitamin D deficiency, all participants took a calcium citrate caplet daily that includes 400 mg calcium and 500 IU vitamin D (Bayer AG, Leverkusen, Germany) beginning 2 weeks before the study and lasting for the duration of the study. After the 2-week equilibration period, study participants were randomly assigned to three groups and asked to consume: (1) one capsule containing 392 mg of blackcurrant powder (low BC group); (2) two capsules containing 392 mg blackcurrant powder per capsule, total 784 mg of blackcurrant powder (high BC group); or (3) one placebo capsule (control group) daily for 6 months. Each 392 mg blackcurrant extract contained 176 mg anthocyanins (min. 40% delphinidin-3-rutinoside, 35% cyanidin-3-rutinoside, 10% delphinidin-3-glucoside and 7% cyanidin-3-glucoside). One capsule was equivalent to about 142 fresh blackcurrants. The blackcurrant powder and composition information was provided by Just the Berries, New Zealand (Just the Berries PD Corporation, Los Angeles, CA, USA). The placebo was

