an identical-looking capsule that contained rice powder (supplied by Beehive Botanicals Hayward, WI, USA). The extract and placebo were encapsulated in vegetarian capsules and packaged into coded containers for daily dosing to participants (Beehive Botanicals Hayward, WI). Distribution of the supplements was performed blindly at the study center at month 0 (study visit 1: after the 2-week equilibration period) and month 3 (study visit 2).

Aside from the exclusion of dietary supplements, foods extremely rich in anthocyanins (all berries, grapes, red wine, and berry juices), and fermented dairy products containing viable *Bifidobacteria* or *Lactobacilli*, all participants were instructed to keep their usual dietary habits for the duration of the study. Subjects provided a 12-h fasting blood sample and stool specimen at each study visit at months 0, 3, and 6 for biochemical and metagenome sequencing analysis, and a physical examination (height, weight, waist circumference, blood pressure) was conducted at the initial visit (month 0), month 3, and the end of the treatment period (month 6). This clinical trial was registered at ClinicalTrials.gov (NCT04431960). The proposed project and its procedures were reviewed and approved by the University of Connecticut Institutional Review Board (HR20-0035) prior to the initiation of the project.

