### *2.4. Bone Density Assessments*

BMD analyses were conducted at the University of Connecticut Korey Stringer Institute by a licensed radiologic technician at baseline and 6 months using DXA (GE Healthcare Lunar) equipped with appropriate software for whole-body, head, arms, legs, trunk, ribs, spine, and pelvis BMD. Specific positioning and analysis guidelines were followed according to the operator's manual. Calibration, maintenance, and quality control of the equipment were routinely conducted following the maintenance instructions in the manual.

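### The marker dose-versus-control comparisons are unadjusted t-tests on percent change at an unstated visit: valid singly, but they leave collected baseline information unused (low priority)

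*Combined protocol and SAP*

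**What the plan says.** Section 3 (Statistical Analysis) describes two analyses of the outcomes.

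- **Mixed model.** PROC MIXED estimates "main and interaction effects of the two factors, treatment (0, 392, or 784 mg/day blackcurrants), and time (baseline, 3 months, and 6 months"). The same section adds: "The significance of changes in all outcome variables was tested by repeated-measures ANOVA", with treatment between subjects and time within subjects. Month 0 is therefore a level of the time factor, that is, an outcome. No covariate is listed and no dose-versus-control contrast is named.
- **Pairwise comparisons.** "Percent changes in BMD and bone biomarkers between control and low BC groups and between control and high BC groups were evaluated" by t-tests. This is the only place where low dose against control and high dose against control are named. The visit is not given.

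On measurement times, section 2.4 has BMD assessed "by a licensed radiologic technician at baseline and 6 months using DXA", so percent change in BMD can only run from month 0 to month 6. The markers have three visits: "Fasted blood samples were collected at months 0, 3, and 6" (section 2.5), and they are assayed "at baseline, 3 months, and 6 months were measured in serum using commercially available ELISA kits" (section 2.6). Section 2.2 has supplements first handed out at month 0, after the equilibration period ("Distribution of the supplements was performed blindly at the study center at month 0"), so the month-0 visit is the baseline.

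Section 1 makes whole-body BMD the primary endpoint and gives the markers the role of explaining mechanism. Section 2.1 gives 40 women recruited. No sample-size calculation, SD, correlation or effect size appears.

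**The concern.** A two-sample t-test on percent change fixes the weight given to baseline instead of estimating it, works on the raw ratio scale, and uses the variance from two of the three arms. When baseline and follow-up are only moderately correlated, subtracting or dividing by baseline adds noise that a covariate would remove.

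The mixed model as described does not supply the adjustment. With month 0 as a free time level, its BMD interaction test is an unadjusted analysis of change. Its marker interaction is an omnibus test over three arms and three visits, which gives no estimate for each dose.

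What is at stake is precision for the markers. Forty women in three arms is about 13 or 14 per arm before drop-out, and the study asks about dose. In addition, a reader cannot tell whether a marker percent change refers to month 3 or month 6.

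**Working it through.** The plan states no power or effect figure, so there is nothing of its own to reproduce.

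**Inputs from the documents:** 40 women, three arms, two-sided 0.05, markers at months 0, 3 and 6, BMD at months 0 and 6.

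**Assumed inputs:** allocation 14/13/13 with no drop-out; markers lognormal with log-SD 0.4, equal correlation rho among visits, and a log difference of 0.35 (a 42% rise) in one dose arm; BMD normal with mean 1.1 and SD 0.10 g/cm², and a difference of 0.02 in one dose arm.

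**Step 1, variance.** With equal SDs, change from baseline has variance 2(1 − rho)σ² and the baseline-adjusted value has (1 − rho²)σ². The ratio adjusted/change is (1 + rho)/2. Estimating the slope costs on average a factor 1 + 1/(37 − 2) = 1.029, with 37 within-arm degrees of freedom.

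| rho | (1 + rho)/2 | with slope cost |
|---|---|---|
| 0.5 | 0.750 | 0.771 |
| 0.7 | 0.850 | 0.874 |
| 0.8 | 0.900 | 0.926 |
| 0.9 | 0.950 | 0.977 |
| 0.95 | 0.975 | 1.003 |
| 0.98 | 0.990 | 1.018 |

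The advantage has gone by about rho 0.95.

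**Step 2, one case by hand (rho 0.5).** √(1/14 + 1/13) = 0.385. SE of pooled log change = 0.4 × √1 × 0.385 = 0.154. SE adjusted = 0.4 × √0.75 × 0.385 × √1.029 = 0.135. The non-central t gives power of 60.0% on 37 df and 71.1% on 36 df.

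**Step 3, simulated marker power at month 6** (100,000 trials per setting, Monte Carlo SE at most 0.16 points), moving one step at a time from the planned t-test to the adjusted contrast:

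| rho | percent-change t-test | two-arm log change | pooled three-arm log change | plus baseline covariate | added by the covariate |
|---|---|---|---|---|---|
| 0.5 | 55.9% | 58.6% | 59.7% | 71.2% | 11.5 |
| 0.7 | 78.9% | 80.4% | 81.5% | 86.3% | 4.8 |
| 0.8 | 92.5% | 93.1% | 93.8% | 95.2% | 1.4 |
| 0.9 | 99.8% | 99.8% | 99.9% | 99.9% | 0.0 |

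The rest of each gap (3.8 of 15.3 points at 0.5) comes from the log scale and pooling. At 0.8 and 0.9 power is near its ceiling. With a smaller log difference of 0.2 the covariate adds 5.7, 4.3, 3.2 and 0.8 points.

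Mean 95% CI half-width on the log scale, pooled change v adjusted, is 0.310 v 0.272, 0.240 v 0.225, 0.196 v 0.189 and 0.139 v 0.137: narrower by about 12%, 6%, 4% and 1%.

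**Step 4, validity.** With no effect (log-SD 0.3 and 0.5, rho 0.5 and 0.8, 14/13/13 and 10/10/10), the percent-change t-test rejects 4.6–5.0% and the adjusted contrast 4.9–5.2%.

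**Step 5, BMD power:**

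| rho | planned interaction F | percent-change t-test | adjusted contrast | adjusted minus F |
|---|---|---|---|---|
| 0.95 | 34.3% | 34.5% | 35.8% | +1.5 |
| 0.98 | 72.4% | 69.7% | 70.8% | −1.6 |
| 0.99 | 95.7% | 93.5% | 94.0% | −1.7 |

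**The case against.** The strongest reply is that the t-tests are not the only planned test. The repeated-measures interaction covers all outcomes. With an equal effect at months 3 and 6 and a log difference of 0.35, its power for the markers is 65.2%, 86.8% and 96.9% at rho 0.5, 0.7 and 0.8, against 71.2%, 86.3% and 95.2% for the adjusted month-6 contrast. On that comparison the adjusted contrast leads only at 0.5. This stands as a limit on the size of the gain. It does not remove the point, because the F test is omnibus and yields no estimate or interval for a dose. An adjusted average over months 3 and 6, which uses both follow-up visits as the F test does, reaches 86.9%, 95.2% and 98.9%.

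It also stands that this is a pilot, that the markers are secondary, and that every correlation here is assumed.

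Three stronger readings are tempting, and the documents support none of them.

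- **The percent-change tests are invalid.** They are not: each holds its 5% level in the simulations. Multiplicity over doses and markers is a separate matter.
- **The primary BMD analysis should be replaced.** Step 5 shows no material gain, and with two scans its visit is not ambiguous.
- **Month 0 as a time level dilutes the efficacy result.** Only the treatment main effect is diluted, to half of the effect for BMD (two visits) and two thirds for a constant marker effect (three visits). The planned interaction is not diluted, and section 3 does not call the main effect the efficacy result.

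**Conclusion.** The point holds for the secondary serum markers, as a matter of efficiency and clarity. The named dose comparisons are valid singly, but they leave out baseline values already in hand and do not state their visit. Under the assumptions above, the covariate itself is worth about 11.5 points of power at correlation 0.5, about 5 at 0.7, 1.4 at 0.8 and none at 0.9, judged at month 6. The documents do not say where in that range the markers lie.

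For whole-body BMD, provided the correlation is about 0.95 or higher, adjustment brings no material gain and may cost up to about 2 points against the planned interaction test. The planned BMD analysis can stand. Low priority.

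**What to change.** **Markers only.** Fit one three-arm PROC MIXED model of log month-3 and month-6 values on treatment, time, treatment × time, log baseline and log baseline × time, with unstructured covariance. State low-versus-control and high-versus-control at month 6 as the marker comparisons, with the month-3/6 average as a named supporting contrast. Report back-transformed ratios with 95% CIs. Keep percent change as a descriptive display and state its visit.

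**BMD.** Keep the planned analysis and add a 95% CI for each dose-versus-control change.

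**Cost.** A few lines of SAS and SAP wording, and no new data. The model spends one error degree of freedom per visit, and readers see ratios in place of raw percent changes. Section 3 is written in the past tense. If the results are already analysed, report the adjusted contrasts beside the planned tests as a labelled post-hoc sensitivity analysis.

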### **2.1. Study Participants**

Forty peri- and postmenopausal women aged 45–60 were initially recruited from northeastern Connecticut through newspaper advertisements, flyers, and email. The inclusion criteria for this study were: (1) women aged 45–60 years old; (2) not on HRT for at least one year before the initiation of the study; (3) maintaining normal exercise level (<7 h/week) and willing to avoid exercise 24-h prior to blood and stool sampling and 12-h prior to bone measurements; (4) willing to ingest a dietary blackcurrant supplement or placebo as well as 400 mg calcium and 500 IU vitamin D daily; (5) willing to avoid other dietary supplements for the duration of the study, (6) willing to avoid intake of foods extremely rich in anthocyanins and fermented dairy products, (7) willing to have 3 blood draws and 2 bone scans and (8) willing to take a urine pregnancy test before each bone scan. Exclusion criteria included: (1) those with metabolic bone disease, renal disease, cancer, cardiovascular disease, diabetes mellitus, respiratory disease, gastrointestinal disease, liver disease, or other chronic diseases, (2) heavy smokers (>20 cigarettes/day), (3) perimenopausal women with any chance or plan of pregnancy, (4) taking prescription medications known to alter bone and Ca metabolism; (5) taking anabolic agents; (6) alcohol consumption exceeding 2 drinks/day. Subjects who met the recruitment criteria upon initial phone screening were immediately invited to the study laboratory at the University of Connecticut in Storrs, Storrs, CT, USA.

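### Dose-versus-control t-tests on percent change use neither the collected baseline value as a covariate nor the third arm, so they give up a little precision in a pilot of about 40 women

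*Combined protocol and SAP*

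**What the plan says.** Section 3 (Statistical Analysis) describes two layers of analysis.

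- A PROC MIXED / repeated-measures analysis of variance is used "to determine the main and interaction effects of the two factors, treatment" and time, set up "with treatment as levels of between-subjects factors and time as levels of within-subjects factors". No other term is named.
- Each dose is then compared with control: "Percent changes in BMD and bone biomarkers between control and low BC groups and between control and high BC groups were evaluated using" t-tests. No covariate is named here either.

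Baseline balance is handled by significance tests: "The significance of differences in baseline characteristics was tested by ANOVA or" a chi-square or Fisher's exact test. No adjustment is tied to their result.

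Section 1 makes whole-body BMD the primary endpoint and calls the study a pilot that also assessed feasibility. Section 2.4 has BMD measured "by a licensed radiologic technician at baseline and 6 months using DXA", so every scanned woman has a baseline value.

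Section 2.1 opens with "Forty peri- and postmenopausal women aged" 45 to 60. Section 2.2 says: "After the 2-week equilibration period, study participants were randomly assigned to three groups". The readable text mentions no stratification. Menopausal stage is not said to have been recorded, although Section 2.2 notes: "The participants were also interviewed about their medical history and dietary behaviors by study personnel".

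**The concern.** The dose-versus-control comparisons bear directly on the stated aim of studying dose-dependent effects. A two-group t-test on change from about 13 women per arm discards two things already in hand: the third arm's information about the residual variance, and whatever the baseline value says about later change. Dividing by baseline to form a percent change is not covariate adjustment. It imposes a fixed scaling and does not estimate how change depends on baseline.

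At stake is some precision, plus the effect of a chance imbalance in the one allocation that occurred. With arms this small such imbalances are common, and the planned baseline tests have little power to flag them. The sample also mixes peri- and postmenopausal women, so stage is a second candidate covariate, but on weaker ground than the baseline value.

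**Working it through.** **Inputs.** From the documents: 40 women recruited (Section 2.1), three arms (2.2), BMD at baseline and 6 months (2.4), two-sided 0.05 (3). The documents give no arm sizes, SD, effect size or power calculation, so there is no stated figure to reproduce. Assumed: arms of 13 (control), 13 (tested dose) and 14, all 40 analysed; a true difference of 1.1 SD of change; and a baseline-change correlation r of 0 or 0.3. The figures are for BMD. The biomarker t-tests have the same form, but no figure is offered for them.

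**1. Residual degrees of freedom.** t-test: 13 + 13 − 2 = 24. Three-arm model: 40 − 3 = 37. With the baseline value: 36.

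**2. Pooling the third arm.** Noncentrality = 1.1 × √(13/2) = 2.804. Critical values are 2.064 (24 df) and 2.026 (37 df). Power is 0.768 for the t-test and 0.780 for the three-arm model, a gain of about 1.2 points.

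**3. Adding the baseline value.** The variance is multiplied by about (1 − r²)(1 + 1/35), the second factor being the average price of estimating one slope with 36 df. The critical value is 2.028.
- r = 0: factor 1.029; noncentrality 2.804/√1.029 = 2.765; power 0.768. This is level with the t-test and about 1 point below the three-arm model without the covariate.
- r = 0.3: factor 0.91 × 1.029 = 0.936; noncentrality 2.804/√0.936 = 2.899; power 0.805, about 4 points above the t-test.

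**4. Simulation (40,000 trials per cell).**

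| r | t-test | three-arm | three-arm + baseline |
|---|---|---|---|
| 0 | 0.767 | 0.780 | 0.767 |
| 0.3 | 0.766 | 0.778 | 0.802 |

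With stage effects of various sizes added, the gain over the t-test at r = 0.3 stays between 3.3 and 3.7 points. With no treatment effect, rejection over all allocations is 0.048 to 0.051 for every model, the t-test included.

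**5. Chance imbalance in baseline.** The standard error of a difference in baseline means is √(2/13) = 0.392 SD. At r = 0.3, an imbalance of that size moves the change contrast by 0.3 × 0.392 = 0.118 SD, or 0.3 of its standard error. At r = 0 it moves nothing.

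**6. Menopausal stage, as a secondary check.** Further assumptions: 20 of 40 women in each stage, and a stage difference in 6-month change of 0.33, 0.5, 0.67 or 1.0 within-stage SD.
- A stage gap of at least 30 percentage points has a 13–17% chance for one dose-control pair and 21–27% for either dose.
- Given 5/13 against 9/13, the unadjusted type I error is 5.5, 6.0, 6.6 and 8.0% in that order of stage difference; with stage in the model it is about 5%. Fisher's test on those counts gives p = 0.24.
- A gap of 3 women gives about 5.1–5.6%; gaps of 0 to 2 give about 3–5%. For a 13-versus-13 pair, gaps of 3 or fewer make up about 83% of allocations. Averaged over gaps of 4 or more, the error is about 7.7% at a stage difference of 0.67 SD and 10.8% at 1.0 SD.
- Power of the three-arm model without and with stage: 0.780 and 0.768 if stage has no effect; 0.772 and 0.770 at 0.33 SD; 0.758 and 0.771 at 0.5; 0.733 and 0.765 at 0.67; 0.681 and 0.766 at 1.0. Break-even is near 0.33 SD.

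**The case against.** The strongest reply is that nothing here is an error. Randomisation makes the t-tests valid, and that stands in full.

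The second is that the plan's own model already does part of the job. With two BMD time points, the treatment-by-time interaction compares change across three arms, so pooling is available and baseline enters as a time level. That also stands, with a limit: baseline is then part of the outcome and not a covariate, and the dose-versus-control comparisons that are actually specified are the t-tests. Against three-arm contrasts without the covariate, adding baseline is worth only −1.3 points (0.780 to 0.767) at r = 0 and +2.4 points (0.778 to 0.802) at r = 0.3.

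Third, this is a pilot reported in the past tense, so a change is likely to be post hoc. That lowers the consequence but does not remove the case for a cheap supporting analysis.

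A reader might go further and infer that mixing menopausal stages biases the dose comparisons, or that stage must be in the model. The documents do not support this. They give no stage mix and no rate of change by stage, and do not say that stage was recorded. The raised conditional error needs both a prognostic stage and a chance gap of about 4 women in 13 or more. A stage range that starts at 0.33 SD also leaves out the case where stage does not matter, in which the stage term costs about 1 point.

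**Conclusion.** The point holds as a modest efficiency matter. The planned dose-versus-control t-tests are valid but use two of the three arms and no baseline covariate. Under the assumed arms of 13/13/14 and a 1.1 SD effect, the adjusted three-arm model is level with them if baseline is unrelated to change and gains about 3 to 4 power points if the correlation is 0.3. That correlation is an assumption, because the documents give none.

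It should not be read as systematic bias or an inflated overall type I error; both are protected by randomisation. Menopausal stage is a reasonable sensitivity covariate, but whether it matters here cannot be settled from the documents. The change is worth considering and is not needed for the t-tests to be valid.

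**What to change.** In Section 3, replace the two sets of t-tests with dose-versus-control contrasts from one three-arm model of 6-month change (or 6-month value), with treatment and the baseline value of that outcome as terms. With baseline in the model, absolute change and final value give the same treatment contrasts. If this is added after unblinding, label it post hoc and show it beside the original t-tests.

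**Cost.** One residual degree of freedom (37 to 36 if all 40 are analysed): about 1 power point against a three-arm model without the covariate, and roughly nothing against the planned t-test, if baseline is unrelated to change. No new data are needed.

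**Optional.** If stage was recorded or can be recovered from the medical-history interview, report it by arm and add it as a covariate in a sensitivity analysis. This costs about 1 further point if stage has no effect and breaks even near a stage difference of 0.33 within-stage SD. If stage cannot be recovered, say so as a limitation.

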**NCT number: NCT04431960**

**Document data: September 29, 2023**

## **Study Protocol and Statistical Analysis Plan**

### **1. Purpose/Introduction:**

This study aimed to evaluate the dose-dependent effects of blackcurrant supplementation on bone density in adult women and its relationship to bone metabolism. The feasibility of the pilot clinical study was also assessed. For this purpose, we conducted a pilot double-blind, randomized, placebo-controlled clinical study with blackcurrant supplementation for six months in peri- and early postmenopausal women aged 45–60. The primary endpoint was whole-body BMD. In addition, to delineate the underlying mechanisms of the action, changes in serum markers of bone metabolism following blackcurrant supplementation were also assessed.

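### Regional BMD sites and serum markers are judged at an unadjusted p < 0.05 with no ordering or exploratory label, so a false significant secondary or mechanism result has a substantial chance of appearing

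*Combined protocol and SAP*

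**What the plan says.** Section 1 names one primary endpoint: "The primary endpoint was whole-body BMD". It gives the serum markers a separate purpose: "to delineate the underlying mechanisms of the action, changes in serum markers of bone metabolism".

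Section 2.4 lists what the DXA software reports: "whole-body, head, arms, legs, trunk, ribs, spine, and pelvis BMD". That is seven regional sites besides whole body, scanned at baseline and month 6. Section 2.6 lists five markers (P1NP, BALP, OC, CTX1 and sclerostin), measured at baseline and at two follow-up visits.

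Section 3 has three elements that matter here:

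- One threshold, with no restriction to the primary endpoint: differences at two-sided p < 0.05 "were considered significant".
- A repeated-measures ANOVA on every outcome variable.
- In a separate sentence, the comparisons of each dose with control: "Percent changes in BMD and bone biomarkers between control and low BC groups and between control and high BC groups were evaluated using" t-tests.

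No section gives a multiplicity adjustment, a testing order, a rule that the ANOVA must be significant before the t-tests are read, or an exploratory label for the regional sites or markers.

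**The concern.** The plan names a single primary endpoint but then gives every other BMD site and marker the same right to be called significant. With many comparisons at 5% each, some will cross the line by chance.

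Two features make this more than a formality. First, the markers are there to explain how the supplement works, so a chance marker result could readily be read as mechanism. Second, the regional sites overlap: ribs, spine and pelvis lie within the trunk, and all sites lie within whole body. One chance deviation can therefore appear at several sites and look like corroboration. In a pilot, such results could also steer the choice of endpoint for the next trial.

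**Working it through.** The documents state no power or familywise error figure, so there is none to reproduce.

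**Inputs from the documents**

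- Threshold: 0.05 two-sided per test (section 3).
- Comparisons per outcome: 2, each dose against control (section 3).
- Regional sites: 7, with one change each, baseline to month 6 (section 2.4).
- Markers: 5, with one change each (month 6) or two (months 3 and 6) (section 2.6). Section 3 does not say which.
- Women recruited: 40 (section 2.1), in three arms (section 2.2).

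**Assumptions, because the documents are silent**

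- Arms of 13, 13 and 14, with the control arm shared by both comparisons.
- Correlations from 0 to 0.9 within the regional sites and within the markers, and 0.5 between months 3 and 6 for a marker. The two families are independent of each other.
- BMD in the t-test sentence includes the regional sites.

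**Number of tests**

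- Regional: 7 × 2 = 14.
- Markers at month 6: 5 × 2 = 10. Markers at both visits: 5 × 2 × 2 = 20.
- Total: 14 + 10 = 24, or 14 + 20 = 34.

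**Expected false positives with no effect on any outcome**

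- 24 × 0.05 = 1.2, or 34 × 0.05 = 1.7. Correlation does not change these.

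**Chance of at least one false positive if the tests were independent**

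- 1 − 0.95^24 = 0.708.
- 1 − 0.95^34 = 0.825.
- Month-6 markers alone: 1 − 0.95^10 = 0.401.

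**Chance of at least one with a shared control and correlated outcomes**

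Simulated pooled two-sample t-tests: 20,000 null trials per setting for the 24 and 34 tests, and 40,000 for the ten marker tests.

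| Correlation, regions / markers | 24 tests | 34 tests | 10 month-6 marker tests |
|---|---|---|---|
| 0 / 0 | 0.69 | 0.79 | 0.38 |
| 0.3 / 0.3 | 0.64 | 0.76 | 0.36 |
| 0.5 / 0.5 | 0.58 | 0.70 | 0.31 |
| 0.7 / 0.5 | 0.53 | 0.66 | 0.31 |
| 0.7 / 0.7 | 0.49 | 0.61 | 0.26 |
| 0.9 / 0.9 | 0.35 | 0.45 | 0.18 |

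Arm size hardly matters: with 10 per arm and 24 tests the chance is 0.68, 0.58 and 0.49 at correlations of 0, 0.5 and 0.7.

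These figures leave out the ANOVA tests that section 3 also plans. Adding the treatment and treatment-by-time tests for the 12 outcomes to the 24 t-tests gives 0.84 at correlation 0, 0.75 at 0.5 and 0.51 at 0.9.

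**After adjustment**

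Benjamini-Hochberg within two families (14 regional tests; 10 month-6 marker tests) brought the chance of any false claim to about 7% to 9% in total over the correlations tried (regions 0.3 to 0.8, markers 0.3 to 0.5). This fits two families each held at 5%: 1 − 0.95² = 0.0975 if independent. It applies when no outcome is truly affected.

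**The case against.** The strongest reply is that this is a pilot of forty women with feasibility among its aims, one named primary endpoint, and markers introduced as an addition. Formal adjustment of secondary outcomes in such a study is debatable, and at about 13 per arm it costs power that has not been quantified. That stands, and is why adjustment should not be the leading remedy. It does not excuse the missing exploratory label: the plan attaches the word significant to any result below 0.05.

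The count is also an inference. No sentence says that each regional site is t-tested, or that month-3 marker changes are. This stands too, and is why three counts are shown.

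A reader might infer four stronger things that the documents do not support:

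- *That a false positive is more likely than not.* With 24 t-tests the chance falls to about one half or below once correlations reach roughly 0.7 in both families. With 34 it falls below one half at 0.9. Nested sites make high correlation plausible, and the documents give no values.
- *That section 3 compares each dose with control on every outcome variable.* That scope belongs to the ANOVA sentence. The t-test sentence covers BMD and bone biomarkers only, so stool metagenome features should not be added to the count.
- *That a null whole-body result would be expected to bring one or two significant sites or markers.* The calculation assumes no effect anywhere and does not condition on the primary result. Regional sites correlate with whole body, so conditioning lowers the figures. With correlations of 0.8 for BMD and 0.5 for markers, the chance is 0.45 for 24 tests (0.87 false positives on average) and 0.57 for 34 (1.36).
- *That a chance marker result will be stated as mechanism.* The plan creates that opening but contains no rule requiring it.

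**Conclusion.** The omission is real and plain from section 3. Beyond whole-body BMD, nothing limits which results may be called significant. The number of false results expected when nothing works is 1.2 for 24 tests and 1.7 for 34. The chance of at least one is roughly 35% to 70% and 45% to 80% respectively. If only the ten month-6 marker tests count, it is about 25% to 40% for marker correlations up to 0.7, and 18% at 0.9.

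The counts of 24 and 34 rest on reading BMD as including the regional sites. The probabilities also rest on assumed arm sizes and correlations, and on no adjustment being intended, which is inferred from the plan's silence. Even the lowest of these figures is well above 5%. The point concerns secondary and mechanism outcomes only; the two dose comparisons on whole-body BMD are a separate matter. It should be corrected, but it does not undermine the primary analysis.

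**What to change.** In section 3:

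1. Confine the statement that p < 0.05 is significant to whole-body BMD.
2. State that the regional BMD sites and all serum markers, at months 3 and 6, are exploratory. Report dose-minus-control estimates with 95% CIs and no significance label.
3. State that no mechanism claim will rest on an unadjusted marker p-value.
4. Say which BMD sites and which marker visits enter the t-tests.
5. If the sponsor wishes to call any of these outcomes significant, do so only after Benjamini-Hochberg or Holm adjustment across both doses, within the regional family and within the month-6 marker family. Say when the families were defined. The document is dated September 2023 and describes the study in the past tense, so families set now may be post hoc.

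The cost is a few sentences and no new data. The downside is that some regional or marker results lose the nominal significant label and, if adjustment is chosen, some power.
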